**Cybex isokinetic dynamometer:**

The testing procedure will be conducted at 60° knee flexion in accordance with the device instructions. Humantrak software will be used to determine peak knee extensor torque.

For both devices, three maximal efforts will be performed on each leg with verbal encouragement to 'push as hard as possible' for five seconds, which is sufficient time to generate peak torque. Subjects will rest for 60-seconds between attempts, monitored with a timer (18). The highest value from the three efforts for each device will be used as the primary outcome for each subject.

**6.4.1 Informed Consent**

Informed consent will be gained by the principal investigator ([name]) and co-investigators ([name] and [name]), as authorised by the Chief Investigator and Principal Investigator.

The participant must personally sign and date the latest approved version of the informed consent form before any study specific procedures are performed. Written and verbal versions of the participant information and informed consent will be presented to the participants detailing no less than:

- the exact nature of the study
- the implications and constraints of the protocol
- the potential side effects and any risks involved in taking part.

It will be clearly stated that the participant is free to withdraw from the study at any time for any reason without prejudice or impact on future care, and with no obligation to give the reason for withdrawal. The participant will be allowed as much time as required to consider the information, and the opportunity to question the Investigator, their GP or other independent parties to decide whether they will participate in the study.

Written informed consent will then be obtained by means of participant dated signature and dated signature of the person who presented and obtained the informed consent. The person who obtained the consent must be suitably qualified and experienced and have been authorised to do so by the Chief/Principal Investigator. A copy of the signed Informed Consent will be given to the participants. The original signed form will be retained at the study site.

#### **6.4.2 Screening and Eligibility Assessment**

Hospital staff and patients (18 years or older) will be recruited by direct invitation or word of mouth. Patients that have undergone ACL reconstruction, who are already scheduled for force testing on the isokinetic dynamometer will be invited to have additional testing using inline dynamometry. Potential participants will be initially screened via telephone or face to face interview to confirm eligibility. Once signed consent is obtained, participants will be invited to attend testing sessions in a physiotherapy department at Liverpool University Hospitals.

#### **6.4.3 Baseline Assessments**

The following demographics will be recorded routinely at baseline:

Gender, age, weight, height, leg dominance, Tegner activity score (TAS).

Pain at rest, measured by a 0-10 numerical rating scale (NRS), will be recorded before initiation of testing. Lever length and force measurements will be recorded during testing.

#### **6.4.4 Randomisation and Codebreaking**

For both the reliability and validity studies, the order of testing will be randomised to account for fatigue and learning effect using the random.org website (<https://www.random.org/>).

Subject numbers will be assigned sequentially as each subject enters the study. Subjects and assessors will be blinded to the force measurement results until testing is complete on each device. Lever length will be measured and recorded by each individual assessor.

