#### Reliability:

A convenience sample of 20 healthy subjects (10 legs) will be recruited from Liverpool University Hospital to determine the inter- and test-retest reliability of the inline dynamometer. The testing procedure will be standardised between assessors. Subjects and assessors will be blinded to the results until all testing is completed.

Subjects will be tested by assessors A and B at the first assessment to determine inter-rater reliability. Assessor A is a physiotherapy knee specialist with 17 years clinical experience and three years clinical experience using HHD. Assessor B is a specialist physiotherapist with 8 years clinical experience but no previous experience using HHD. The order of testing will be randomised to account for fatigue and learning effect using the random.org website (<https://www.random.org/>).

To determine test-retest reliability, measurements will be repeated by assessor A seven days after the index testing. All tests will be performed at the same time of the day, with subjects encouraged to continue their usual weekly exercise between testing sessions, but to avoid significant changes in training loads, which may affect fatigue levels and their ability to generate force.

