**Validity:**

A convenience sample of 44 patients that have undergone ACL reconstruction will be recruited from Liverpool University Hospitals NHS Foundation Trust to determine the validity of the inline dynamometer versus Iso-ED. Inline dynamometry will be performed by Assessor A and Iso-ED performed by Assessor C (15 years' experience). The order of testing will be randomised to account for fatigue and learning effect. Subjects and assessors will be blinded to the results until all testing is completed.

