## **9. STATISTICS**

### **9.1 Description of Statistical Methods**

Inter and test-retest reliability will be calculated using intra-class correlation coefficients (ICC) with 95% confidence intervals (CI) and illustrated using a Bland & Altman plot. Standard error of measurement (SEM =  $[SD\sqrt{1-ICC}]$ ) and the minimal detectable change (MDC) ( $1.96 \times \sqrt{2} \times SEM$ ) will be calculated to verify the absolute error of the instrument and the smallest change considered significant respectively.

ICC values will be considered as follows: < 0.69: weak reliability, 0.70–0.79 reasonable reliability, 0.80–0.89 good reliability, and 0.90–1.0 excellent reliability

Validity will be calculated using ICC (95% CI), Pearson product moment correlation (Pearson-r) and illustrated using Bland & Altman plot.

Pearson values of coefficients will be established as follows: < 0.5 indicated weak validity, 0.5–0.75 indicated moderate to good validity, and > 0.75 indicated excellent validity.

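### Test order is randomised because of fatigue and learning, but no balance is stated and no analysis in 9.1 includes order, so any order effect counts as rater or device error

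*Combined protocol and SAP*

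**What the plan says.** Section 6.4.4 states that in the reliability and validity studies "the order of testing will be randomised to account for fatigue and learning effect using the random.org website". Both halves of section 6.1 say the same: order of assessors A and B for 20 healthy participants, and order of the two devices for 44 patients. None of these places mentions blocking, counterbalancing or a target split. For test-retest, "measurements will be repeated by assessor A seven days after the index testing"; assessor B does not take part in that session.

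Section 9.1 lists the whole analysis. Reliability rests on the ICC with its confidence interval, a Bland-Altman plot, the SEM and the MDC. For validity, "Validity will be calculated using ICC (95% CI), Pearson product moment correlation (Pearson-r) and illustrated using Bland & Altman plot". No model has a term for order, and no check for an order effect is planned.

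Section 6.4 contains safeguards: a warm-up, three graded practice trials on each device, 60 seconds between attempts and 10 minutes between devices. It states no rest between the two assessors in the reliability study, where both use the same device.

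**The concern.** The plan treats fatigue and learning as real threats and relies on randomised order to deal with them. For a comparison of means that would largely do. Here the main results are measures of spread. If the second test differs systematically from the first, the paired difference moves one way in participants tested in one order and the other way in the rest. The two shifts cancel in the mean but not in the variance.

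Section 9.1 would therefore report that variance as disagreement between raters or devices. A clinician using one device once would not meet it, because it comes from testing twice in one session. At stake are an ICC that is too low, limits of agreement that are too wide, and an MDC that is too large, so that some real change in a patient could be dismissed as measurement error.

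**Working it through.** **Inputs.** From the documents: 20 and 44 participants (6.1), the SEM and MDC formulas, and the ICC and Pearson bands (9.1). The plan has no figure for an order effect, so there is nothing of its own to reproduce. Assumed: an order effect δ (second minus first test) common to all participants, one order per participant, and r = δ / SDd, where SDd is the SD of paired differences without an order effect. The range r = 0.25, 0.5, 1.0 is illustrative.

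**Spread.** The paired difference is bias + sδ + error, with s = +1 or −1 by order. With an even split,

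Var(difference) = SDd² + δ² = SDd²(1 + r²),

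so the limits of agreement widen by √(1 + r²).

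**ICC.** Set the total variance to 1, the ICC without an order effect to ICC₀, and E = 1 − ICC₀. Then SDd² = 2E and δ² = 2Er². Order moves one of a participant's scores up by δ/2 and the other down by δ/2. This adds δ²/4 = Er²/2 to the variance of each score and takes the same amount from their covariance:

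ICC = (ICC₀ − Er²/2) / (1 + Er²/2).

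For ICC₀ = 0.90 this is (0.9 − 0.05r²)/(1 + 0.05r²). For ICC₀ = 0.95 it is (0.95 − 0.025r²)/(1 + 0.025r²).

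**SEM and MDC.** Putting the new SD and ICC into the 9.1 formula gives SEM² = E(1 + r²), so the SEM and MDC grow by the same factor as the limits.

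| r | Limits, SEM, MDC multiplied by | ICC from 0.90 | ICC from 0.95 |
|---|---|---|---|
| 0.25 | 1.031 | 0.894 | 0.947 |
| 0.5 | 1.118 | 0.877 | 0.938 |
| 1.0 | 1.414 | 0.810 | 0.902 |

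**Does an order term remove it?** A simulation (4,000 runs, ICC₀ = 0.90, simple randomisation, δ = 0.2 of the total SD, so r² = 0.04/0.2 = 0.2) gave these values in units of the total SD:

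- n = 20: SEM 0.341 without the term and 0.311 with it; MDC 0.946 and 0.863.
- n = 44: SEM 0.345 and 0.315; MDC 0.956 and 0.872.

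The formula predicts a ratio of √1.2 = 1.095; the SEM ratios are 1.096 and 1.095.

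**Uneven splits.** If simple randomisation is used (an assumption), exact binomial probabilities are:

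- n = 20: exactly 10:10, 17.6%; 14:6 or worse, 11.5%. A 14:6 split puts (14 − 6)/20 = 40% of δ into the mean rater difference.
- n = 44: exactly 22:22, 12.0%; 28:16 or worse, 9.6%. A 28:16 split puts 12/44 = 27% of δ into the mean device difference.

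At r = 0.5, a 14:6 split moves the mean by 0.4 × 0.5 = 0.20 SDd. The standard error of that mean is about 1/√20 = 0.22 SDd.

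**Test-retest.** Assessor A is first or second at the index session but tests alone a week later. If the lone retest behaves like a first test (an assumption), retest minus index moves by δ in size where A was second at index, and by nothing otherwise. With half in each position this adds δ²/4 to the variance. The limits then widen by √(1 + r²/4), or 0.8%, 3.1% and 11.8% for the three values of r, with SDd now that of the test-retest differences. The mean moves by δ/2 even when the positions are balanced.

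**The case against.** The strongest reply is that the effect may be small. The practice trials, the 60-second and 10-minute rests, and the use of the best of three efforts are aimed at fatigue and learning. At r = 0.25 the limits widen by 3% and the ICC falls by 0.006. Nothing in the documents supports a large r. This stands, except that no rest between assessors is stated for the reliability study.

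It also stands that the error is conservative: it cannot make a poor device look good. Nor does 9.1 set an acceptance limit for the Bland-Altman results.

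A reader might infer that the device would lose its *excellent* grade. That depends on starting exactly at the 0.90 cut-off. From 0.95, the ICC stays above 0.90 even at r = 1.0. Sampling error at a true ICC of 0.90 is also larger than the likely shift. Using Fisher's z with standard error 1/√(n − 1.5), estimates range over about 0.77 to 0.96 at n = 20 and 0.82 to 0.94 at n = 44. If the two devices have equal variances, Pearson's r falls as the ICC does, so from 0.90 it would stay above the 0.75 cut-off for the top validity band.

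A reader might also infer that the orders will be unbalanced, or that the mean difference is biased. The documents are silent on balance, and randomising removes expected order bias from the mean rater or device difference.

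**Conclusion.** The mechanism holds. Order is randomised but left out of the analysis, so any order effect stays in the within-subject variance. It inflates the SEM, MDC and limits of agreement and lowers the inter-rater and validity ICCs, even with a perfect split. Test-retest is affected too, through assessor A's position at the index session.

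The size is unknown. Over the assumed range of r, the inter-rater and validity limits widen by 3% to 41%, and an expected ICC of 0.90 falls to between 0.894 and 0.810; the lower end of r is plausible given the safeguards. These figures assume a constant order effect and an even split, and the split probabilities assume simple randomisation.

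The documents do not support saying that the design is unbalanced or that the device will be misgraded. This is a minor improvement, worth making because it is cheap and uses what the study already randomises.

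**What to change.** 1. In 6.4.4, specify blocked order lists: 10:10 for the reliability study and 22:22 for the validity study. Balance protects the mean rater and device differences but does not remove the extra variance, so step 3 is the essential part.
2. Add test order to the CRF. No section says that it is recorded; the items listed in 6.4.3 do not include it.
3. In 9.1, add test order (first or second) as a fixed effect in the model that gives the inter-rater and validity ICCs, and the SEM and MDC. For the Bland-Altman results, regress each paired difference on order coded +1 and −1. Take the bias from the intercept and the limits as the intercept ± 1.96 residual SDs.
4. For test-retest, adjust for assessor A's position at the index session. A first-or-second term would not help there, because it coincides with index versus retest.
5. Report the mean second-minus-first difference, so that readers can see whether order mattered.

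The cost is one CRF field and one degree of freedom per analysis (with one difference per participant, 18 in place of 19 and 42 in place of 43). No extra participants or tests are needed. The term assumes the same order effect in everyone; fatigue that varies between patients would remain in the error.

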#### **6.4.5 Subsequent assessments**

Torque measurements for the participants in the test-retest reliability study will be repeated one week after index testing. At each visit, an eligibility check will be conducted (i.e., change to circumstances).

### **6.5 Definition of End of Trial**

The end of trial is defined as the point when all subject data has been collected for the reliability and validity studies and analysis of this data has been completed.

### **6.6 Discontinuation/ Withdrawal of Participants from Study Treatment**

Each participant has the right to withdraw from the study at any time. In addition, the investigator may discontinue a participant from the study at any time if it is considered necessary for any reason including:

- The subject becomes pregnant
- Ineligibility (either arising during the study or retrospectively having been overlooked at screening)
- Significant protocol deviation
- Significant non-compliance with study requirements
- An adverse event which requires discontinuation of the testing procedure or results in an inability to continue to comply with study procedures
- Disease progression which requires discontinuation of the study device or results in inability to continue to comply with study procedures
- Consent withdrawn
- Lost to follow up

Withdrawal from the study will result in exclusion of the data for that participant from analysis. In the healthy participant cohort, withdrawn participants will be replaced unless the withdrawal was due to an adverse event that was directly associated with the testing procedure. The reason for withdrawal will be recorded in the CRF.

If the participant is withdrawn due to an adverse event, the investigator will arrange for follow-up visits or telephone calls until the adverse event has resolved or stabilised.

## **6.7     Source Data**

Source documents are original documents, data, and records from which participants' CRF data are obtained. These include, but are not limited to, hospital records containing medical history and surgical information. All documents will be stored safely in confidential conditions. On all study-specific documents, other than the signed consent, the participant will be referred to by their personal identification number (PIN), not by name.

## **7.       TREATMENT OF TRIAL PARTICIPANTS**

### **7.1       Description of Study Intervention(s)**

For the reliability study, healthy subjects will be tested by two assessors at the index testing session, with three trials performed per assessor per leg. Testing will be repeated by one examiner, one week after index testing.

For the validity study, ACL subjects will be tested by two assessors with the two different devices, with three trials performed per assessor per leg. The highest score from the three trials per device will be used for analysis.

## **7.2 Maintenance and storage of device**

The inline dynamometer and accessories will be stored in a customised, protective case. Between testing sessions, this device will be stored in a locked room, accessible only to the Principal Investigator. The Cybex isokinetic dynamometer is a fixed device and remains in the physiotherapy department at Broadgreen hospital.

# **8. SAFETY REPORTING**

## **8.1 Reporting of AE**

All AE's occurring during the study observed by the investigator or reported by the participant, whether or not attributed to the device under investigation will be recorded on the CRF, as specified in the protocol. All ADE's will be recorded in the CRF.

The following information will be recorded: description, date of onset and end date, severity, assessment of relatedness to device and action taken. Follow-up information will be provided as necessary.

The relationship of AEs to the device will be assessed by a medically qualified investigator or the sponsor/manufacturer and will be followed up until resolution or the event is considered stable.

All ADEs that result in a participant's withdrawal from the study or are present at the end of the study, will be followed up until a satisfactory resolution occurs.

Where relevant, any pregnancy occurring during the clinical study and the outcome of the pregnancy, will be recorded and followed up for congenital abnormality or birth defect.

## **8.2 Reporting Procedures for All SAEs/ SADEs/ UADEs**

As the devices are CE marked, all SAE/SADE/UADEs will be reported to the sponsor/legal representative and manufacture and LUHFT R&D **within one working day** of the investigator team becoming aware of them.

Reports of related and unexpected SAEs will be submitted to ethics within 15 days of the Chief Investigator becoming aware of the event, using the SAE report form for non-CTIMPs published on the NRES website.

All reporting to LUHFT R&D will be signed by the PI or Co-investigator.

### **8.3 Annual Reports**

In addition to the above reporting the Chief Investigator will submit once a year, throughout the trial, or on request a progress/safety report to the REC and R&D.

## **9. STATISTICS**

### **9.1 Description of Statistical Methods**

Inter and test-retest reliability will be calculated using intra-class correlation coefficients (ICC) with 95% confidence intervals (CI) and illustrated using a Bland & Altman plot. Standard error of measurement (SEM =  $[SD\sqrt{1-ICC}]$ ) and the minimal detectable change (MDC) ( $1.96 \times \sqrt{2} \times SEM$ ) will be calculated to verify the absolute error of the instrument and the smallest change considered significant respectively.

ICC values will be considered as follows: < 0.69: weak reliability, 0.70–0.79 reasonable reliability, 0.80–0.89 good reliability, and 0.90–1.0 excellent reliability

Validity will be calculated using ICC (95% CI), Pearson product moment correlation (Pearson-r) and illustrated using Bland & Altman plot.

Pearson values of coefficients will be established as follows: < 0.5 indicated weak validity, 0.5–0.75 indicated moderate to good validity, and > 0.75 indicated excellent validity.

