## 2. SYNOPSIS

Measurement of peak knee extensor torque is important following anterior cruciate ligament (ACL) reconstruction. Isometric electromechanical dynamometry (Iso-ED) is the gold standard method of measuring peak knee extensor torque, but access to this equipment is limited due to the associated expense and lack of portability. Inline 'pull-type' dynamometry is an alternative measure that is more affordable, portable and less time consuming, but this device has not been adequately investigated for reliability or validity. This study will investigate the reliability and validity of an inline 'pull-type' dynamometer for measuring peak knee extensor torque in patients following ACL reconstruction. For the reliability study, healthy volunteers will be assessed by two assessors (inter-rater) at the index testing session, with testing repeated by one assessor one week later (test-retest). Validity will be investigated against Iso-ED as the gold standard. The results of this study will help to determine whether inline dynamometry can be recommended as a reliable and valid means of measuring knee extensor torque in clinical practice.

Study Title	Reliability and validity of inline 'pull-type' dynamometry for measuring peak knee extensor torque in patients following anterior cruciate ligament (ACL) reconstruction.
Internal ref. no.	R&D SP0558
Type of study	Clinical investigation of a medical device
Trial Design	Prospective, cross sectional study using a within-participant, repeated measures design.
Trial Participants	Healthy participants recruited from staff at LUH for reliability study Patients who have had ACL reconstruction at LUH for validity study
Planned Sample Size	20 participants for reliability study 44 participants for validity study
Follow-up duration	One week for reliability study No follow up required for validity study
Planned Trial Period	6 months
Primary Objective	To determine the reliability and validity of inline 'pull-type' dynamometry for measuring peak knee extensor torque
Secondary Objectives	To determine comfort levels when testing using different devices
Primary Endpoint	Peak knee extensor torque, recorded in Newton-metres, measured with inline dynamometry and isometric electromechanical dynamometry
Secondary Endpoints	Pain during testing measured with a numerical rating scale

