#### 4. BACKGROUND AND RATIONALE

Lower limb strength testing is utilised in various settings including surveillance of uninjured athletes (1), patient monitoring during rehabilitation and determining readiness to return-to-play (RTP) following anterior cruciate ligament reconstruction (ACLR) (2). Knee extensor muscle weakness is associated with an increased risk of re-injury and reduced functional performance following ACLR (3-5) and is a modifiable risk factor for knee osteoarthritis (6). Knee extensor strength deficits may be present in those that pass functional RTP tests (e.g., hop for distance) (5, 7, 8), highlighting the importance of quantifying knee extensor strength specifically.

Isometric electromechanical dynamometry (Iso-ED) is the gold standard method for quantifying knee extensor strength (indicated by peak isometric torque) (9), with hand-held dynamometry (HHD) considered an alternative measure that is more affordable, portable and less time consuming (10). 'Push-type' HHD requires belt stabilisation for stronger subjects (10-13) and demonstrates similar peak isometric torque generating capacity to Iso-ED when performed at approximately 90° knee flexion in healthy volunteers (14). However, peak knee extensor torque occurs at 60-70° knee flexion (15), which is difficult to measure using belt-stabilised 'push-type' HHD due to slippage of the device or a non-perpendicular force being applied to the gauge (16). When compared directly, 'push-type' HHD performed at approximately 90° knee flexion overestimated limb symmetry in subjects with various knee joint impairments and could not be recommended as a direct substitute for Iso-ED at 60° knee flexion (16).

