To date, only one study has investigated the reliability and validity of HHD for measuring peak knee extensor torque in patients following ACLR (17). 'Push-type' HHD performed isometrically at 90° knee flexion was shown to have excellent test-retest reliability (ICC: 0.98) and 100% specificity for detecting a limb symmetry index (LSI) >10%, but only moderate to good validity ( $r=0.62$ ) versus isokinetic dynamometry. Although LSI is recommended as an objective, criterion-based guideline for return to running (18) or RTP (2) following ACLR, leg dominance or dysfunction of the reference limb may overestimate the capacity of the side being measured, potentially leading to a premature return to high-risk activities and subsequent re-injury (19). Peak isometric knee extensor torque normalised to body weight is an alternative means of determining whether an individual has achieved target values associated with positive knee-joint function following ACLR ( $\geq 3.0-3.1$  Nm/kg) (20, 21). Mean peak torque values in the aforementioned study were 1.67 ( $\pm 7.4$ ) Nm/kg and 2.03 ( $\pm 7.9$ ) Nm/kg for isometric HHD and isokinetic testing respectively, indicating a lower force generating capacity for 'push-type' HHD. In addition, since the reference values were

obtained isokinetically (60°/sec), it is likely that the validity of 'push-type' HHD would be lower if Iso-ED was used as the reference standard.

Inline dynamometers allow isometric knee extensor torque to be measured at peak angles (i.e., 60-70°), but the reliability and validity of this 'pull-type' dynamometry has not been adequately evaluated (10, 22). The objective of this study therefore is to determine the reliability and validity of inline 'pull-type' dynamometry for measuring peak isometric knee extensor torque in patients following ACLR. We hypothesise that inline dynamometry is a reliable and valid measure of peak isometric knee extensor torque when performed at 60-70° knee flexion, using Iso-ED as the gold-standard reference.

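### The only validity grades are tied to Pearson r, which cannot see systematic under-reading, so a device that reads low could still be graded as having excellent validity

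*Combined protocol and SAP*

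**What the plan says.** Section 9.1 names three tools for validity: "Validity will be calculated using ICC (95% CI), Pearson product moment correlation (Pearson-r) and illustrated using Bland & Altman plot". It then attaches grades to one of them. The scale opens "Pearson values of coefficients will be established as follows: < 0.5 indicated weak validity" and continues with 0.5 to 0.75, "indicated moderate to good validity, and > 0.75 indicated excellent validity".

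A separate set of bands, introduced by "ICC values will be considered as follows", appears earlier in the section, and each band is worded as a grade of reliability. The plan does not say whether these bands also grade the validity ICC. It does not say whether any ICC is for absolute agreement or consistency, or for single or average measurements. The Bland-Altman plot is for illustration, with no acceptable mean difference or limits of agreement. No rule says which statistic decides the conclusion.

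The Synopsis gives the purpose: to help determine "whether inline dynamometry can be recommended as a reliable and valid means of measuring knee extensor torque in clinical practice", with isometric electromechanical dynamometry (Iso-ED) as the reference.

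**The concern.** The question is whether two devices agree, but the graded statistic measures association. Pearson r shows whether patients are ranked and spaced alike on both devices. It does not show whether the two readings are the same.

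The Background itself treats systematic error as important. It reports that push-type testing "could not be recommended as a direct substitute for Iso-ED" at 60° knee flexion, and describes an earlier push-type result as "indicating a lower force generating capacity". It also says: "Peak isometric knee extensor torque normalised to body weight is an alternative means of determining whether an individual has achieved target values", citing 3.0 to 3.1 Nm/kg. A device can rank patients very well and still place many of them on the wrong side of a figure like that.

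The plan also contains a possible source of such error. Torque is force times lever length (Section 6.2), and for the inline device lever length is taken with a tape measure (Section 6.4). A consistent 5% error in lever length makes torque 5% wrong in every patient, and r would not change.

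At stake is a published grade of excellent validity for a device that reads systematically low.

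**Working it through.** The plan computes no agreement figure, so there is none to reproduce. The sample size in Section 9.2 does not bear on this point.

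**1. Algebra.** Let the reference and inline readings have variances vx and vy, covariance c and mean difference b.

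- Pearson r = c / √(vx·vy). It does not contain b, and rescaling either device leaves it unchanged.
- Consistency ICC = 2c / (vx + vy). It does not contain b either.
- Absolute-agreement ICC = 2c / (vx + vy + b²). It falls as b grows.
- Bland-Altman limits = b ± 1.96·√(vx + vy − 2c).

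Only the last two respond to a constant offset. Section 9.1 ties neither to a validity grade.

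**2. Inputs for an illustration.** The Background gives means of 1.67 (push-type) and 2.03 Nm/kg (isokinetic), so the shortfall is (2.03 − 1.67)/2.03 = 17.7%. That comes from another device type, at 90°, against another reference mode, with r = 0.62. It is a convenient size, not a forecast for the inline device. Assumed, because the documents do not give them: reference mean 2.6 Nm/kg, between-patient SD (s) 0.5 to 0.8, random error SD (e) 0.15 to 0.25, with the error either all in the inline device or split equally between devices.

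**3. Two corners at 17.7%** (factor k = 0.823, error all in the inline device). Here vx = s², vy = k²s² + e², c = ks², b = −0.177 × 2.6 = −0.46, b² = 0.212.

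- s = 0.8, e = 0.15: vx = 0.640, vy = 0.456, 2c = 1.053. r = 0.527/√(0.640 × 0.456) = 0.975. Consistency ICC = 1.053/1.096 = 0.96. Absolute ICC = 1.053/1.308 = 0.805.
- s = 0.5, e = 0.25: vx = 0.250, vy = 0.232, 2c = 0.4115. r = 0.206/√(0.250 × 0.232) = 0.85. Consistency ICC = 0.4115/0.482 = 0.85. Absolute ICC = 0.4115/0.694 = 0.59.

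**4. All corners:**

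| Under-reading | Pearson r | Absolute-agreement ICC |
|---|---|---|
| 0% | 0.89–0.98 | 0.89–0.98 |
| 5% | 0.88–0.98 | 0.86–0.97 |
| 10% | 0.87–0.98 | 0.77–0.92 |
| 17.7% | 0.85–0.98 | 0.59–0.81 |

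Pearson r is in the top band in every row. It drops slightly only because the random error is held fixed while the signal shrinks.

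**5. Consequence at 3.0 Nm/kg** (bivariate normal, same inputs). On the reference, 21–31% of patients are at or above 3.0. With 17.7% under-reading, 64–90% of those read below it. In all, 18–21% of patients are misclassified, against 5–11% with no bias. With a reference mean of 2.03 instead of 2.6, 2–9% of all patients are misclassified and the absolute ICC is 0.67–0.86.

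**6. Constant offset at n = 44.** In 2,000 simulated trials per setting (true r 0.90; SDs taken as 0.74 and 0.79, because the printed 7.4 and 7.9 are implausible beside those means), offsets of 0, −0.36, −0.75 and −1.0 Nm/kg gave r above 0.75 in at least 99.9% of trials. The mean consistency ICC stayed at 0.89. The mean absolute ICC was 0.89, 0.80, 0.60 and 0.48.

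**7. Is r just above 0.75 close agreement?** With equal variances and no bias, r = 0.75 gives limits of ±1.96·√(2 × 0.25) = ±1.39 SDs of the readings. At SDs of 0.5 to 0.8 that is about ±0.7 to ±1.1 Nm/kg.

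**The case against.** The strongest reply is that the plan already contains the right tools. An ICC is listed first for validity, a Bland-Altman plot exists to show bias, and Section 9.5 promises raw data as supplementary material. An offset would be visible in the report. That stands: the risk is a favourable label beside contrary evidence, not hidden evidence. But neither tool is tied to a validity grade, and a consistency ICC would miss a constant offset.

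Several narrower points also stand in part:

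- The direct-substitute remark concerns push-type testing and limb symmetry, and a proportional error equal in both legs cancels in a symmetry ratio. The primary outcome, however, is torque in Nm for each leg.
- No analysis against 3.0 Nm/kg is planned, and the 18–21% figure depends on an assumed mean of 2.6. It shows what an offset could do and should not drive the severity.
- At 5% under-reading, the absolute-agreement ICC hardly moves.
- The two scales conflict only if the reliability bands are carried over to validity. In that case, with no bias and equal variances (ICC equal to r), 0.76 to 0.79 is excellent on one scale and reasonable on the other. The plan does not say whether they carry over.
- The Pearson bands allow comparison with the earlier ACL study. Reporting r descriptively keeps that comparison.

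**Conclusion.** The concern holds. Followed as written, Section 9.1 can award its top validity grade to a device that reads systematically low. This follows from the wording and the algebra and needs none of the assumed values.

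The size of the effect does depend on assumptions. At an under-reading of 17.7%, borrowed from a different device, r remains at 0.85–0.98 while the absolute-agreement ICC is 0.59–0.81. At 5% the practical difference is small. The documents do not say which is nearer the truth for the inline device.

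Naming the ICC form would not be enough by itself. At 17.7% the absolute ICC can still reach about 0.81, which is good on the reliability bands. A limit on the difference is needed too. This should be fixed before analysis; it does not undermine the design.

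**What to change.** In Section 9.1:

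- Specify a two-way, absolute-agreement, single-measurement ICC with 95% CI for validity.
- State that the validity conclusion rests on this ICC together with the Bland-Altman mean difference and 95% limits of agreement, each with a 95% CI.
- Judge these against a maximum acceptable difference in Nm, the unit of the primary outcome, set by the sponsor before the data are seen.
- Report Pearson r as a descriptive measure of association and remove its validity grades.
- Use the same ICC form for inter-rater and test-retest reliability. The standard error of measurement and minimal detectable change are computed from the ICC, and a systematic difference between an experienced assessor and one new to the method would escape a consistency ICC.

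Precision is adequate. With one value per patient and n = 44, the 95% CI half-width is t/√n = 0.304 SDs of the differences for the mean difference, and t·√(1/n + 1.96²/(2(n−1))) = 0.524 SDs for each limit. These multipliers apply in Nm or Nm/kg. For an SD of differences of 0.15 to 0.29 Nm/kg they give about ±0.05 to ±0.09 and ±0.08 to ±0.15 Nm/kg. If both legs enter the analysis, the within-patient pairing must be allowed for.

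The cost is a few lines of text and analysis, a prior commitment to an acceptable difference, and possibly a less favourable grade. Design, sample size and data collection do not change.
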